# 11.2 Study Endpoints

## 11.2.1 Primary Effectiveness Endpoint

The primary effectiveness endpoint is the cumulative consumption of opioids from the time of hospital discharge to 6 weeks post-TKA Surgery. Opioid consumption will be converted to morphine equivalents and subject consumption will be verified by pill count at follow-up visits. The cumulative morphine equivalent will be divided by the number of days to provide the Total Daily Morphine Equivalent (TME) for the subject.

The difference in the average TME between the two treatment groups will be calculated as Active TME average - Sham TME average, such that a positive difference indicates that the Active Treatment Group had a larger average TME than the Sham Treatment group, while a negative value indicates the opposite. A negative difference between treatment groups reflects a positive outcome for the study.

A superiority hypothesis test using the two-independent sample t-test will be used to statistically evaluate the difference in the average TME between the two treatment groups. A confidence interval for the difference in the average TME between the two treatment groups will be provided to assist in the interpretation of the results.

The Primary Effectiveness Study Objective is met when the average TME for the Active Treatment group is less than the average TME for the Sham Treatment group, and the resulting ttest is statistically significant using a one-sided  $\alpha = 0.025$  level of statistical significance

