# **Protocol Synopsis**

Title	A Post-Market, Multi-Center, Prospective, Double-blind, Randomized, Controlled Study to Evaluate the iovera° Device in Treating Pain Associated with Total Knee Arthroplasty				
Study Device	iovera° (myoscience Inc., Fremont, CA)				
Study Objective	To evaluate the outcomes of patients undergoing iovera° treatment of the ISN and AFCN prior to total knee arthroplasty to provide temporary postoperative pain relief				
Study Design	Multi-center, prospective, randomized				
Treatment Groups	Pre-operative iovera° treatment vs. pre-operative sham iovera° treatment				
Duration of Participation	Up to 16 weeks (12 weeks post-op)				
Study Population	Male or female, ages 22 to 79 scheduled to undergo a total knee replacement as a result of osteoarthritis				
Total Number of Subjects	150 subjects				
Number of Sites	Up to 8 sites				
Study Procedures	iovera° treatment introducing temporary nerve conduction block of the ISN and AFCN				
Data Collection Tools	
 
WOMAC
 
SF-36
 
PROMIS
 
NRS for Pain
 
				
Primary Endpoint	Cumulative Opioid Consumption at 6 weeks post-TKA Surgery				
Secondary Endpoints	
 
Length of Hospital Stay
 
WOMAC Pain
 
WOMAC Function
 
Physical Performance (Measured by: Range of Motion, 30 Second Chair Test and 40 Meter Walk Test)
 
				

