Due to the mechanism of action, iovera° introduces a new mode of pain management delivery in TKA. The iovera° system uses liquid nitrous oxide contained within the device and closed-end needles to create a precise zone of cold at the target nerve sites. This Focused Cold TherapyTM delivery platform causes a temporary peripheral nerve block based on a process called Wallerian degeneration (2nd degree axonotmesis) without disrupting connective nerve tissue. With nerve conduction blocked, pain is relieved in sensory nerves (nerves that pass impulses from receptors toward or to the central nervous system). Degeneration of the nerve axons is followed by a predictable restoration of nerve function involving axon regeneration from the point of treatment to the distal end of the nerve at a rate of 1.0–1.5 mm a day. Early clinical study results have demonstrated that the duration of effect of iovera°, when applied to the infrapatellar branch of the saphenous nerve for knee pain, is two to three months; longer than that of other clinically adopted modalities (PCA opioids, single shot regional nerve blocks, continuous regional nerve blocks, extended-release peri-operative local opioids, oral and IV NSAIDs, acetaminophen, and oral opioids). Early clinical data further suggests that iovera°, when applied to the infrapatellar branch of the saphenous nerve (ISN) and anterior femoral cutaneous nerve (AFCN) prior to TKA, reduces the amount of opioids requested by subjects to maintain similar levels of pain relief.

This study is designed to investigate whether iovera° treatment prior to TKA decreases cumulative patient opioid use over the course of 6 weeks following TKA while maintaining similar levels of pain relief. The study will also investigate whether there is a relationship between patients treated with iovera° and length of hospital stay; patient reported pain and function as measured by WOMAC; and improved physical rehabilitation as measured by functional performance measures and range of motion.

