#### 10. STUDY PROCEDURES

## 10.1 Overview

An Overview of the study visits is shown in **Figure 3**. Eligible Subjects are randomized to iovera° treatment or to sham treatment with the iovera° device. The primary endpoint is cumulative opioid consumption at 6 Weeks Post-TKA.

Figure 3. Overview of Study Visits

- \*Screening and Treatment can occur on the same day.
- \*\*Data collected retrospectively, iovera° Treatment may be same day as TKA.

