# 10.6 Visit 3 / Total Knee Arthroplasty (Day 0)

The Investigator or Designee will confirm their ability to safely perform TKA within the following protocol requirements. All surgical and in-patient data, safety information including adverse event assessments, will be collected retrospectively from hospitalization records:

- Pre-operative History & Physical Exam, including assessment of the target knee, must be documented in the medical record and included as study data.
- Surgery and Implant Medial parapatellar surgical approach; cruciate-retaining or posterior-stabilized TKA; all surfaces replaced.
- Pre-emptive analgesia medications administered prior to TKA, orally, intravenously, or otherwise, for the purpose of pain management before, during, or after surgery, are to be recorded in the medical record and included as study data.
- Procedural anesthesia during Arthroplasty this will be limited to spinal anesthesia, the formulation, or "cocktail," of medications used are to be recorded in the medical record and included as study data.
- Local Infiltration Analgesia permitted per surgeon or anesthesia preference, the formulation, or "cocktail," of medications used are to be recorded in the medical record and included as study data.
- Regional nerve block for post-operative analgesia single shot Adductor Canal Block required, the formulation, or "cocktail," of medications used are to be recorded in the medical record and included as study data.
- Post-operative analgesia opioid or other pain medications used are to be recorded in the medical record and included as study data
- Other data to be collected retrospectively from hospitalization medical records include: Time of admission to and discharge from the hospital, Length of surgery, Method of wound closure, Tourniquet use, Blood loss, Post-operative drain use, and Adverse Events, including Opioid-related adverse events - sedation, dizziness, nausea, vomiting, constipation, physical dependence, tolerance, and respiratory depression.

Outpatient analgesia – The subject will be required to bring all of their unused prescription narcotic medications dispensed during study participation to all study follow-up visits for

pill count. Any other over-the-counter analgesic medications or other pain relief therapies used (per patient report) will also be recorded by the study coordinator, or designee, at each follow-up visit.

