# 10.7.1 Visit 4/2 Weeks Post-op (14 ±3 Days), Visit 5/4 Weeks Post-op (28 ±5 Days), and Visit 6/6 Weeks *Post-op (42 ±5 Days)*

Subjects will be evaluated and data collected per the schedule of events. Any changes in concomitant medications/concurrent procedures will be documented. Any anticipated observations, adverse events, adverse device effects and/or SAE/UADE/USADE will be assessed and documented. Photographs may be taken of the treatment area.

The Subject will complete a WOMAC questionnaire, NRS for Pain when standing from a seated position, PROMIS questionnaire, and SF-36 questionnaire. Subjects will be asked to assess their treatment assignment (the blind).

Subjects will answer Satisfaction questions at Visit 6.

The subject will complete the Physical Performance Measures in the following order under supervision of the investigator or designee:

- Active Range of Motion
- 40 Meter Walk Test
- 30 Second Chair Test

Detailed instructions for the conduct of these performance measures are included in the Study Operations Manual. Assistive/ambulatory device usage and work status will also be assessed.

Utilization of healthcare services post-discharge, or since the previous follow-up visit, will be assessed. Subjects will be asked to report any Secondary Surgical Interventions, Emergency/Urgent care visits, Unscheduled physician office visits, and other healthcare services used since their last study visit. Investigators will also record any additional or unscheduled services performed at follow-up visits (examples include knee aspiration, unscheduled x-ray, other unscheduled diagnostic procedures, etc.).

Subjects will be asked to bring all prescription opioid bottles to all study follow-up visits. A pill count will be completed by the study coordinator, or designee, and opioid medication will be redispensed to subjects.

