**Table 3. Schedule of Assessments** 

Table 5. Schedule of Assessments							
	Visit 1 / Screening	Visit 2 / iovera° Treatment	Visit 3 / DAY OF TKA (Day 0)	Visit 4 / 2 Weeks Post-op	Visit 5 / 4 Weeks Post-op	Visit 6 / 6 Weeks Post-op	Visit 7 / 12 Weeks Post-op
Assessment Informed Consent	X						
	X	v					
Eligibility	X	X					
Medical history Concomitant medication	X	A					
assessment	X	X	X	X	X	X	X
Prior/Concurrent Therapy	X	X		X	X	X	X
Randomization*		X					
Study Treatment		X X X X					
Physical Exam		X					
Vital signs	X	X					
Knee Circumference		X					
PROMIS Questionnaire	X			X	X	X	X
WOMAC Questionnaire	X			X	X	X	X
SF-36	X			X	X	X	X
NRS for Pain	X			X	X	X	X
Work Status Questions	X			X	X	X	X
Subject Satisfaction Questions						X	X
Assessment of Blind		X		X	X	X	X
Physical Performance Measures	X			X	X	X	X
Pain Medication Accountability				X	X	X	X
AE/SAE Assessment		X	X	X	X	X	X
Photographs (if applicable)		X		X	X	X	X

\* Randomization occurs after the subject has met eligibility criteria and prior to or at Visit 2

Follow-up visits generally consist of the following:

- The Investigator or designee assesses the occurrence of health status changes and adverse events since last study visit;
- The Investigator or designee determines whether any changes in daily medications have occurred;
- The Investigator or designee performs drug accountability (pill counts) of postoperative outpatient opioid medication and re-dispenses unused opioid medications to subjects after use. The Investigator or designee records other over-the-counter concurrent pain medication use and pain relief therapies used per subject report;
- The Subject completes a WOMAC questionnaire, an SF-36 questionnaire, PROMIS questionnaire, Work Status Questions, Satisfaction questions (Visits 6 and 7 only),

self-assessment of the blind, and reports NRS for Pain when standing from a seated position;

• The Investigator or designee performs Physical Performance Measures (Range of Motion, 30 Second Chair Test and 40 Meter Walk Test).

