#### 11. STATISTICAL METHODOLOGY AND ANALYSES

#### 11.1 Introduction

This is a prospective, randomized, sham-controlled, multi-center, post-market trial to evaluate the iovera° device in treating pain associated with total knee arthroplasty (TKA). The study is designed to investigate whether iovera° treatment prior to TKA decreases cumulative patient opioid use over the course of 6 weeks following TKA while maintaining similar levels of pain relief.

The study will also investigate whether there is a relationship between patients treated with iovera° and length of hospital stay; patient reported pain and function as measured by WOMAC; patient satisfaction; and improved physical rehabilitation as measured by functional performance measures and range of motion.

The primary safety endpoint is the onset of device-related adverse events through twelve-weeks after TKA surgery. The primary measure of effectiveness is the Total Daily Morphine Equivalent (TME) of pain medications used from Day of Discharge to the 6-week follow-up visit. In addition. Change from Baseline in WOMAC Pain at the 6-week follow-up visit will be evaluated as a secondary endpoint. A variety of secondary effectiveness endpoints, including performance and pain assessments, will be measured.

Up to 8 study sites within the United States will screen a sufficient number of subjects to ensure that 150 subjects (Randomized 1:1 to approximate 75 Active Treatment subjects plus 75 Sham Treatment subjects) will be randomized and treated.

Subjects will be randomized either to receive therapeutic treatment with the iovera° treatment or to receive a sham treatment with the iovera° treatment, using a balanced 1:1 active-to-sham randomization stratified by Study Site.

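### The stated aim is opioid use over the 6 weeks after TKA, but the primary measure counts only from hospital discharge and leaves out inpatient opioids the trial already records

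*Protocol*

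**What the plan says.** - **Aim.** Section 1 asks whether treatment "decreases cumulative patient opioid use over the course of 6 weeks following TKA", and section 11.1 repeats the sentence. Neither place excludes the hospital stay.
- **Labels.** The Protocol Synopsis lists "Cumulative Opioid Consumption at 6 weeks post-TKA Surgery", and section 10.1 says "The primary endpoint is cumulative opioid consumption at 6 Weeks Post-TKA". Neither gives a starting point.
- **Operative definition.** Section 11.2.1 defines the endpoint as "cumulative consumption of opioids from the time of hospital discharge to 6 weeks post-TKA Surgery". The total in morphine equivalents is divided by a number of days to give the daily figure (TME), and that number is not fixed. Section 11.1 describes the same measure as medication "used from Day of Discharge to the 6-week follow-up visit".
- **Inpatient data.** For postoperative analgesia in hospital, section 10.6 says "opioid or other pain medications used are to be recorded in the medical record and included as study data".
- **Outpatient data.** At follow-up visits the site "performs drug accountability (pill counts) of postoperative outpatient opioid medication" (text under Table 3).
- **Visit timing.** Section 10.7.1 sets the 6-week visit at "Post-op (42 ±5 Days"), that is, day 37 to day 47.
- **Length of stay.** It is listed as a secondary endpoint in the Synopsis and in section 11.2.2, and section 11.10 says the study is powered for it.

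**The concern.** TME alone decides whether the Primary Effectiveness Objective is met, so its window determines what a positive result means. There are two problems.

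First, the first postoperative days fall inside the six weeks named by the aim but outside the endpoint. A conclusion about opioid use over the six weeks after surgery would rest on data without the inpatient period. Data collection does not force this, since the inpatient doses are recorded.

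Second, the counting starts at an event that follows randomization and that the trial itself studies as an outcome. If active treatment changes the time of discharge, the two arms are averaged over different stretches of recovery. Part of any difference in TME could then reflect when counting began.

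**Working it through.** **1. The plan's own figure.** Section 11.10 uses a difference of 7.14 mg/day, SD 13.1 mg/day, one-sided α = 0.025 and power 0.80. The normal approximation is 2 × (1.960 + 0.842)² × (13.1/7.14)² = 2 × 7.849 × 3.366 = 52.8, so 53 per group. The exact t-test gives power 0.794 at 53 and 0.801 at 54. The stated 54 per group is reproduced. The calculation does not depend on which window is used, so it neither settles the question nor shows an error.

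**2. The windows side by side.**

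| Place | Start | End |
|---|---|---|
| Aim (1, 11.1) | TKA | 6 weeks after TKA |
| Synopsis, 10.1 | not given | 6 weeks after TKA |
| Primary measure (11.1) | day of discharge | 6-week visit |
| Primary endpoint (11.2.1) | time of discharge | 6 weeks after TKA |

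The two operative statements agree on discharge. The aim is broader than both.

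**3. Assumptions for size.** The protocol gives neither a daily opioid profile nor an expected stay. I assume discharge on day d = 1 to 3, and use that is flat or falls exponentially from day 0 with time constant τ (20, 15 or 10 days). Let U(a,b) be use from day a to day b: b − a if flat, otherwise τ(e^(−a/τ) − e^(−b/τ)). All results are ratios, so dose level cancels.

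**4. Share of day 0–42 use left out,** U(0,d)/U(0,42):

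| Profile | d = 1 | d = 2 | d = 3 |
|---|---|---|---|
| Flat | 2.4% | 4.8% | 7.1% |
| τ = 20 | 5.6% | 10.8% | 15.9% |
| τ = 15 | 6.9% | 13.3% | 19.3% |
| τ = 10 | 9.7% | 18.4% | 26.3% |

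This share is left out in both arms. It is not a difference between arms.

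**5. Effect of a change in stay alone.** Take identical opioid profiles in both arms and let A(d) = U(d,42)/(42 − d) be the daily average from discharge.

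- Flat: A(d) is constant, so the effect is 0%.
- τ = 20: half a day earlier gives +1.7%; a full day gives +3.3%.
- τ = 10, half a day: A(1.5)/A(2) = 0.2088/0.2009 = 1.039, or +3.9%.
- τ = 10, one day: A(2)/A(3) = 0.2009/0.1861 = 1.080, or +8.0%.

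Half a day is a relevant scale. Section 11.10 gives an SD of 1 day and 69 per group for length of stay but no difference. By the t-test approximation the detectable difference is (1.960 + 0.842) × 1 × √(2/69) = 0.48 day.

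**6. The end of the window.** Ending on day 42 gives 42 − 3 = 39 to 42 − 1 = 41 days. Ending at the visit gives 37 − 3 = 34 to 47 − 1 = 46 days. For one subject, the visit-end average divided by the day-42 average is 1.00–1.13 for a visit on day 37 and 0.89–1.00 for a visit on day 47. If visit timing is alike in the arms, this is noise.

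**The case against.** The strongest reply is that sections 11.1 and 11.2.1 agree on a discharge start, so post-discharge use is what the sponsor means. That start is defensible: section 1 separately motivates lower opioid use during outpatient rehabilitation, and pill counts can verify outpatient medication only. The Synopsis and section 10.1 are short labels without a start, so they do not contradict section 11.2.1. All of this stands, and it is why keeping the discharge start is an acceptable repair. It does not rescue the aim sentence, which still promises more than the endpoint delivers. Nor can this be left to the analysis plan, because the mismatch lies within the protocol.

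A reader might also infer four stronger things that the document does not support.

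- **That the end of the window is contradictory.** The week-6 wording can be read as the name of Visit 6. Pill counts happen at visits, the per-protocol cohort used for the primary analysis requires completion of that visit (11.3.3, 11.3.4), and section 11.8 assigns visits through week 6 with a ±5-day window. The two wordings are a minor point.
- **That the comparison is biased by up to 26%.** That figure is the extreme corner of assumed profiles and applies to both arms. With spinal anesthesia and a required nerve block (10.6), a decline starting on day 0 is itself uncertain.
- **That the discharge start favors the device.** If use is flat or declining, earlier discharge can only leave TME unchanged or raise it, so a shorter stay on active treatment would make the comparison conservative.
- **That the sample size is wrong.** It reproduces.

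**Conclusion.** The concern holds in this form: the primary measure does not cover the period named in the stated aim, because it leaves out inpatient postoperative opioids that are already recorded. The mismatch can be read directly from the text and needs no assumption.

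The dependence on length of stay is conditional. It is absent if treatment does not change stay or if use is flat. If use declines, it is about 0–4% of TME per half day and 0–8% per day, with a shorter stay on active treatment working against the device. Those sizes rest on the assumed profiles (flat, or τ down to 10 days) and discharge on days 1–3. The protocol supplies neither, and a profile that rises after discharge would change the direction. This should be fixed before unblinding, since a window chosen afterwards would be open to challenge.

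**What to change.** Choose one of two repairs.

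- **(a) Keep the aim.** Count from the end of surgery to the 6-week end point, including the recorded inpatient opioids, and report discharge-start use as supportive. Cost: converting inpatient doses already in the data, and accepting a mix of chart doses and pill counts.
- **(b) Keep the discharge start.** Restate the aim (sections 1 and 11.1), the Synopsis and section 10.1 labels, and the eventual conclusion as post-discharge use. Prespecify a surgery-start analysis with inpatient opioids as a sensitivity analysis. Cost: mostly wording, plus the same dose conversion for the sensitivity analysis. The window start still depends on length of stay, which is why that analysis is needed.

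Under either, use one end point in sections 11.1 and 11.2.1, and define the denominator as the days actually counted. Ending at the 6-week visit and dividing by actual days is acceptable and needs no apportioning of pill counts. A fixed day 42 is an alternative, but it needs a rule for the pill-count interval that spans that day.

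A separate improvement at no cost, not part of the mismatch: section 10.4 stratifies randomization by center, while section 11.2.1 plans a two-sample t-test. Including site in the primary analysis model would match the analysis to the randomization.

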#### Assessments:

- NRS for Pain when standing from a seated position in target knee
- NRS for Pain when standing from a seated position in the contralateral knee
- PROMIS-29 Profile v2.0 Participant Format
- WOMAC Osteoarthritis Index NRS3.1
- SF-36v2® Health Survey Standard, United States (English)

Physical Performance Measures in the following order:

• Active Range of Motion

- 40 Meter Walk Test
- 30 Second Chair Test

Detailed instructions for the conduct of these performance measures are included in the Study Operations Manual. Assistive/ambulatory device usage and work status will also be assessed.

Subjects may be complete Screening / Visit 1 and iovera° Treatment / Visit 2 on the same day.

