#### 10.4 Randomization

After meeting all of the inclusion and none of the exclusion criteria and prior to study treatment, Subjects will be randomized in a 1:1 manner to either:

- iovera° Treatment: Subject undergoes treatment with the study device using a functioning Smart Tip.
- Sham Treatment: Subject undergoes treatment with the study device using a sham Smart Tip.

Randomization assignments will be stratified by study center with randomly chosen block sizes of 4 or 6. Small but randomly determined block sizes preserve treatment assignment balance within study center while maintaining assignment unpredictability. The Investigator or designee will record the randomization assignment in the source Any Investigator who is discovered to tamper with documentation and eCRF. randomization will be immediately terminated from the study.

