## 11.2.2 Secondary Effectiveness Endpoints

One of the secondary objectives of the study is to show that 6-weeks after treatment the Active Treatment group has a similar amount of pain relief as the Sham Treatment group. Change in WOMAC Pain from the Baseline visit to the six-week visit will be calculated for each subject as:

Change in WOMAC Pain =

6-Week Visit WOMAC Pain – Baseline Visit WOMAC Pain

such that a negative value indicates a decrease in the WOMAC Pain, while a positive value indicates the opposite.

The difference in the average Change in WOMAC Pain between the two treatment groups will be calculated as Active Change in WOMAC Pain average - Sham Change in WOMAC Pain average, such that a positive difference indicates that the Active Treatment Group had a larger average Change in WOMAC Pain than the Sham Treatment group, while a negative value indicates the opposite. Since a negative Change in WOMAC Pain is indicative of pain relief, then a negative difference between treatment groups reflects a positive outcome for the study.

A non-inferiority hypothesis test using the two-independent sample t-test will be used to statistically evaluate the difference in the mean Change in WOMAC Pain between the two treatment groups. A confidence interval for the difference in the average Change in WOMAC Pain between the two treatment groups will be provided to assist in the interpretation of the results.

The objective of this secondary endpoint is to show that the average reduction in WOMAC Pain for the Active Treatment group is not worse than the average reduction for the Sham Treatment group by more than one-half of the common standard deviation for the Change in WOMAC Pain scores. The objective is met when the resulting t-test is statistically significant using a one-sided  $\alpha = 0.025$  level of statistical significance.

A variety of additional secondary effectiveness endpoints will be assessed to further characterize pain relief, functional performance, and range of motion. These include:

- Active Range of Motion
- 40 Meter Walk Test
- 30 Second Chair Test
- Length of Hospital Stay
- WOMAC Scores (Pain, Stiffness, and Function)
- SF-36 Scales and Summary Measures
- PROMIS-29 Profile Domains and Pain Intensity Score
- NRS for Pain

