For each secondary effectiveness endpoint, the result, as well as the Change from Baseline value, will be summarized at each visit the endpoint is collected. Two sets of hypotheses tests will be performed: the paired t-test will be used to evaluate if the Change from Baseline result is statistically different from no change, while the two-independent sample t-test will be used to statistically evaluate the difference between the two treatment groups for both the original result and for the Change from Baseline result. Confidence intervals will be provided to assist in the interpretation of the results.

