#### **Poolability** 11.6

Data will be pooled from multiple study sites for this analysis. The justification for pooling is made on a clinical basis. The basis for pooling comes from three critical factors: the study sites must implement one common protocol; the sponsor must provide monitoring of study site compliance; the study sites must use common data collection procedures.

In addition, poolability across study sites will be assessed by presenting results across study centers and by analyzing treatment-by-site interaction using a two-way analysis of variance with Treatment, Site, and Treatment-by-Site interaction as terms in the model. Assessment of treatment-by-site interaction will be assessed at a 0.15 level of significance. A non-significant interaction effect will support poolability of study sites. A significant treatment-by-site interaction, if deemed to be only quantitative in nature as opposed to qualitative (i.e., if only due to a difference in magnitude of treatment effect across sites as opposed to a difference in direction of treatment effect across sites) will not necessarily disqualify study sites from being pooled. Note that prior to assessing interaction sites with less than 5 subjects will be combined. To avoid the scenario that the data from the combined super-site dominate the trial conclusion, sites with less than 5 enrolled subjects be combined according to their geographical closeness, and once a super-site have five or more enrolled subjects, then the forming of this super-site will stop and the forming of a new super-site will start. Site by treatment interactions of a quantitative nature, (i.e., all sites show the treatment to be beneficial, but perhaps to a different degree by study site) will not be considered to be an impediment to pooling. Site by treatment interactions qualitative in nature (i.e., the vast majority of sites show the treatment to be beneficial, but one or more sites show the treatment to be detrimental) will require extensive evaluation of the sites with contrary results to attempt to determine what factors at those sites led to the result.

<sup>1 Meinert, C. (1986). Clinical Trials: Design, Conduct, and Analysis. Oxford University Press, New York.

<sup>2 Medical Devices Dispute Resolution Panel Meeting of September 6, 2001 (Panel Transcript)

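### The deciding tests for TME and WOMAC Pain omit the stratification factor and the collected baseline, an avoidable loss of precision

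*Protocol*

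**What the plan says.** Protocol 10.4: "Randomization assignments will be stratified by study center with randomly chosen block sizes of 4 or 6". Section 11.1 repeats the stratification and plans up to 8 sites.

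Protocol 11.2.1, primary endpoint: "A superiority hypothesis test using the two-independent sample t-test will be used to statistically evaluate the difference in the average TME". The objective is met when the active mean is lower and "the resulting ttest is statistically significant using a one-sided" level of 0.025. The same test underlies the sample size in 11.10.

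Protocol 11.2.2, WOMAC Pain at 6 weeks: "A non-inferiority hypothesis test using the two-independent sample t-test will be used to statistically evaluate the difference in the mean Change in WOMAC Pain", again at one-sided 0.025. Section 11.10 sets the margin at 11. The baseline is available: the Screening assessments in 10.3 include the "WOMAC Osteoarthritis Index NRS3.1".

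For the other secondary endpoints, 11.2.2 says that "the two-independent sample t-test will be used to statistically evaluate the difference between the two treatment groups for both the original result" and also for the change from baseline.

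Site enters a model only in 11.6, as a "two-way analysis of variance with Treatment, Site, and Treatment-by-Site interaction as terms in the model", and only to judge poolability. Section 11.9 leaves sensitivity analyses to the SAP, not the deciding tests.

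**The concern.** Blocking within site balances the arms inside each site, so differences between sites largely cancel out of the treatment contrast. The unadjusted t-test still counts them in its error term. Its standard error is then larger than the true sampling variation of the estimate, the confidence interval is wider than the design warrants, and the test's actual size falls below 0.025. Site differences in opioid use are plausible here: under 10.6, local infiltration is left to surgeon or anesthesia preference, and post-operative opioids are recorded, not standardized.

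For WOMAC Pain there is a second loss. A change score subtracts baseline with a fixed coefficient of 1, whereas ANCOVA estimates the coefficient. Omitting the baseline covariate leaves the size nominal and costs only power. This is the thinner of the two tests: 11.10 needs 64 analyzable per arm, and about 67 remain after the planned 10% loss.

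Both losses sit in the tests that decide whether the objectives are met, and the data needed to avoid them are already collected.

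**Working it through.** **Inputs from the protocol (10.4, 11.1, 11.10).** TME: difference −7.14 mg/day, SD 13.1. WOMAC Pain change: SD 22, margin 11, expected difference 0. One-sided alpha 0.025, 1:1 allocation, up to 8 sites, blocks of 4 or 6. Randomizing 150 with 10% loss leaves 135, about 67 per arm.

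**Inputs assumed, because the protocol gives none.** Between-site share of TME variance: 0, 5, 10, 20%. Baseline/6-week WOMAC Pain correlation ρ: 0.3 and 0.6. Ratio k of the 6-week SD to the baseline SD: 1, 1.25, 1.5.

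**Step 1: reproduce the stated sizes.** Noncentral t with 2n−2 degrees of freedom and noncentrality δ/(σ√(2/n)):

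- TME, n = 54: 7.14/(13.1 × √(2/54)) = 2.83, power 0.801. At n = 67, power 0.879.
- WOMAC Pain, n = 64: 11/(22 × √(2/64)) = 2.83, power 0.801. At n = 67, power 0.819.

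Both stated sizes are right for the unadjusted tests.

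**Step 2: TME with and without site.** 20,000 simulated trials per scenario: 8 sites of 17 (136 subjects, 68 per arm), permuted blocks of 4 or 6 within site, total SD held at 13.1, effect 0 or −7.14. The pooled t-test is compared with a linear model on treatment and site. Monte Carlo error is about 0.001 on size and 0.002 on power.

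| Assumed between-site share | 0% | 5% | 10% | 20% |
|---|---|---|---|---|
| t-test SE / true SD of the estimate | 1.00 | 1.02 | 1.05 | 1.10 |
| One-sided size, t-test | 0.025 | 0.023 | 0.018 | 0.016 |
| Power, t-test (%) | 88.5 | 89.1 | 89.7 | 91.4 |
| Power, treatment + site (%) | 88.5 | 89.9 | 91.1 | 94.4 |
| 95% CI half-width, t-test (mg/day) | 4.44 | 4.43 | 4.42 | 4.39 |
| 95% CI half-width, treatment + site | 4.45 | 4.34 | 4.23 | 3.98 |

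The t-test's own power rises across the table because total SD is fixed and stratification removes the site part from the estimate. The power gains from modelling site are 0, 0.8, 1.4 and 3.0 points. At a 20% share the interval is 1 − 3.98/4.39 = 9% narrower.

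A separate simulation with 128 subjects and exact balance within site gave t-test sizes of 0.022, 0.019 and 0.016 at 5, 10 and 20%, while the site-adjusted test stayed at about 0.024 to 0.025. A further run gave 0.026 for the t-test at 5%, so the departure from nominal is clear only at 10% and above.

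**Step 3: WOMAC Pain, ANCOVA against change score.** In units of the baseline variance, the change score has variance 1 + k² − 2ρk and ANCOVA has residual variance k²(1 − ρ²). The difference is (1 − ρk)², which is never negative. The ratio is k²(1 − ρ²)/(1 + k² − 2ρk). For k = 1 and ρ = 0.3 this is 0.91/1.40 = 0.65. Power at 67 per arm uses SD 22 × √ratio and 8 fewer degrees of freedom.

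| k | Ratio, ρ = 0.3 | Power | Ratio, ρ = 0.6 | Power |
|---|---|---|---|---|
| 1 | 0.65 | 0.945 | 0.80 | 0.894 |
| 1.25 | 0.78 | 0.900 | 0.94 | 0.841 |
| 1.5 | 0.87 | 0.868 | 0.99 | 0.822 |

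The planned t-test has 0.819 throughout. These figures take no credit for any site effect on WOMAC Pain.

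**The case against.** The planned tests are valid, pre-specified and correctly sized; both keep more than 80% power after 10% loss. A size below 0.025 errs on the safe side. For TME, zero gain lies within the range examined. At a 5% site share the half-width moves only from 4.43 to 4.34 mg/day against an expected effect of 7.14, so a changed conclusion is unlikely. The WOMAC Pain gain rests on an assumed correlation and SD ratio and vanishes as ρk approaches 1. The change score already uses baseline, and 11.3.4 makes only the primary objective decisive. No subject would be spared, because 11.10 needs 69 per arm for Length of Stay. The paired raw and change comparisons of the other secondaries carry no success rule.

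All of this stands, and it limits the point to precision. It does not show that the unadjusted tests are the better choice. The large-sample ANCOVA variance never exceeds the change-score variance, the site model loses essentially nothing when sites do not differ, and 11.10 itself makes similar pain relief the second half of a two-fold objective. The other secondaries are a minor part of the point.

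**Conclusion.** The concern holds as an efficiency point that should be taken up, not as an error in the tests. Omitting site makes the TME test conservative if sites differ, with a power cost of about 0 to 3 points and an interval up to about 9% too wide for site shares up to 20%. Omitting baseline WOMAC Pain leaves the size nominal but forgoes up to 13 points of power (82% to 95%) in the best case examined and almost nothing in the worst. The direction is certain. The size depends on a site variance share, a correlation and an SD ratio that the protocol does not supply. Because 11.2.1 and 11.2.2 tie success to the t-tests, only a change to those sections alters the deciding analyses.

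**What to change.** - **Primary (11.2.1, 11.10):** test TME at one-sided 0.025 in a linear model with treatment and site, combining small sites by the rule already in 11.6, and take the confidence interval from the same model.
- **WOMAC Pain (11.2.2, 11.10):** ANCOVA of the 6-week score on treatment, site and baseline WOMAC Pain, comparing the upper confidence bound with the fixed margin of 11 at one-sided 0.025. Name the value 11 in 11.2.2 in place of half the common SD, so that the margin does not shift with the smaller residual SD.
- **Supportive:** keep both t-tests. The interaction check in 11.6 can stay as it is.
- **Other continuous secondaries with a baseline (not Length of Stay):** one baseline-adjusted between-group comparison per visit in place of the separate raw and change t-tests.

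The cost is wording in three sections, no new data, and about 7 degrees of freedom for site plus 1 for baseline out of about 132. The sample size stays as planned. The change must be made before unblinding.
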